The primary efficacy endpoints were therefore the change in CDAI and DAS28-CRP from baseline 1 (Screening visit of base study SPM-005) and baseline 2 (Day 0 of SPM-006) to each follow-up visit. The time course of the average change in the DAS28-CRP is plotted in **Figure 7**. In this figure the MCID of -1.2 is indicated by the light blue dotted horizontal line. The average change in DAS28-CRP for the All Subjects group remained significantly reduced from baseline 1 (shown as Study Visit Month -3.5) throughout 48 months of follow-up. The group that remained on VNS monotherapy had a larger reduction in DAS28-CRP from baseline 1 than the group that re-initiated biologic therapy.

[figure not shown]

Figure 7: SPM-005/006 DAS28-CRP Change from Baseline

The time course of the average change in the CDAI is plotted in **Figure 8**. The MCID of -12 is indicated by the light blue dotted horizontal line. The CDAI was significantly decreased from baseline 1 (shown as Month -3.5) at the start of SPM-006 and remained decreased throughout 48 months of follow-up.

[figure not shown]

Figure 8: SPM-005/006 CDAI Change from Baseline

Adverse events were recorded from the time of enrollment through end of study. There were no deaths in this study. Nine subjects experienced an SAE, but only 1 SAE was deemed to be device related. The device related TEAE was device pain and discomfort, which ranged from mild to moderate in severity. All 18 subjects reported at least 1 TEAE during the study. There were no significant findings based on review of vital signs, physical examination or other observations in this study.

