May not be reproduced outside of SetPoint Medical without written permission from Document Control.

46 of 111

	
baseline to Week 12, 24, 48, 96, 144 and 192
 
 RAMRIS bone erosion, osteitis, synovitis, and CARLOS score change from baseline to Week 12 and 24 RAMRIS bone erosion progression (> 0.5) rate from baseline to Week 12 and 24 Change in plasma biomarker concentrations (e.g., IL-6, SAA, MMP3) 	
Safety		
To evaluate the safety of the SetPoint System	
Incidence of AEs and SAEs from informed consent to Week 264
 
Incidence of device malfunctions from Implant Procedure to Week 264
	
The incidence of treatment emergent AEs and SAEs that are more common in the treatment group compared to control is a standard measure of the safety. The incidence of device malfunction informs about the device reliability.

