17.6 Analysis of Safety Measures

The incidence of AEs and SAEs from informed consent to Week 264 will be tabulated. Each AE will be coded using the Medical Dictionary for Regulatory Activities (MedDRA) and presented based on the system organ class and preferred term.

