9 SAFETY EVALUATION

9.1 AE and SAEs

The incidence of AEs and SAEs from informed consent date to Week 12 will be tabulated. Each AE will be evaluated by clinical investigators in terms of seriousness, severity (i.e., mild, moderate, severe) and strength of relationship (i.e., not related, unlikely related, probably related, definitely related, indeterminate) to the implant procedure, implant device, stimulation, Energizer, and explant procedure. Any AE that is determined by a participating investigator to be related (definitely related or probably related) to the implant procedure, implant device, stimulation, Energizer, or explant procedure will be categorized as device related. In unblinded analyses, if the subject was assigned to the control group, but the AE indicates relationship to stimulation, the AE relationship will be updated to "not related."

For all AE tables, a subject reporting the same adverse event more than once will be counted once when calculating the number and percentage of subjects with that particular event. If a subject reports the same AE more than once or has the same AE on multiple occasions, the maximum severity grade and relationship will be presented.

The frequencies and percentages of treatment-emergent adverse events will be presented by MedDRA system organ class (SOC) and preferred term (PT). Complete subject listings of all AE will be provided. For each AE the following will be specified: start and stop dates, severity grade, MedDRA SOC and PT, relationship (not related, unlikely related, probably related, definitely related, or indeterminate) to the implant procedure, implant device, stimulation, Energizer, and explant procedure, , as well as action taken, outcome of the adverse event, and seriousness.

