Severe	xx	xx (xx.x%)	xx	xx (xx.x%)	xx	xx (xx.x%)
SAE [1]						
Implant Procedure SAE	xx	xx (xx.x%)	xx	xx (xx.x%)	xx	xx (xx.x%)
Implant Device SAE	xx	xx (xx.x%)	xx	xx (xx.x%)	xx	xx (xx.x%)
Stimulation SAE	xx	xx (xx.x%)	xx	xx (xx.x%)	xx	xx (xx.x%)
Energizer SAE	xx	xx (xx.x%)	xx	xx (xx.x%)	xx	xx (xx.x%)
Explant Procedure SAE	xx	xx (xx.x%)	xx	xx (xx.x%)	xx	xx (xx.x%)

Abbreviations: AE, adverse event; RA, rheumatoid arthritis; SAE, serious adverse event.

Note: AEs coded using the MedDRA dictionary Version 21.0 or later. Given in the table are subject counts and percentages. At each level of summation, subjects are counted only once. Subjects experiencing AEs of more than one severity are summarized according to the maximum severity experienced over all episodes of an AE.

[1] AEs judged to be “Definitely related” or “Probably related” are reported as “Related”.

Reference: Listing 16.x.x.x

SOURCE: xxxxx SAS 9.4 {program location} {run date/time}}

CONFIDENTIAL

119 of 158

May not be reproduced outside of SetPoint Medical without written permission from Document Control.

Table 14.1.3.2
Adverse Events by SOC and Maximum Severity: All Events
Safety Population

SOC Preferred Term	Treatment (N=xxx)				Control (N=xxx)				All (N=xxx)			
	Mild Events n (%)	Moderate Events n (%)	Severe Events n (%)	Total Events n (%)	Mild Events n (%)	Moderate Events n (%)	Severe Events n (%)	Total Events n (%)	Mild Events n (%)	Moderate Events n (%)	Severe Events n (%)	Total Events n (%)
Prior to Implant Procedure												
Any AE [1]	xx x (xx%)	xx x (xx%)	xx x (xx%)	xx x (xx%)	xx x (xx%)	xx x (xx%)	xx x (xx%)	xx x (xx%)	xx x (xx%)	xx x (xx%)	xx x (xx%)	xx x (xx%)
SOC 1 [1]	xx x (xx%)	xx x (xx%)	xx x (xx%)	xx x (xx%)	xx x (xx%)	xx x (xx%)	xx x (xx%)	xx x (xx%)	xx x (xx%)	xx x (xx%)	xx x (xx%)	xx x (xx%)
Preferred Term 1	xx x (xx%)	xx x (xx%)	xx x (xx%)	xx x (xx%)	xx x (xx%)	xx x (xx%)	xx x (xx%)	xx x (xx%)	xx x (xx%)	xx x (xx%)	xx x (xx%)	xx x (xx%)
Preferred Term 2	xx x (xx%)	xx x (xx%)	xx x (xx%)	xx x (xx%)	xx x (xx%)	xx x (xx%)	xx x (xx%)	xx x (xx%)	xx x (xx%)	xx x (xx%)	xx x (xx%)	xx x (xx%)
Preferred Term 3	xx x (xx%)	xx x (xx%)	xx x (xx%)	xx x (xx%)	xx x (xx%)	xx x (xx%)	xx x (xx%)	xx x (xx%)	xx x (xx%)	xx x (xx%)	xx x (xx%)	xx x (xx%)
Preferred Term 4	xx x (xx%)	xx x (xx%)	xx x (xx%)	xx x (xx%)	xx x (xx%)	xx x (xx%)	xx x (xx%)	xx x (xx%)	xx x (xx%)	xx x (xx%)	xx x (xx%)	xx x (xx%)

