7 SAFETY EVALUATION

7.1 AE and SAEs

The incidence of AEs and SAEs in the safety population (see Section 5.2) will be tabulated through Week 264 (end of study). Each AE will be evaluated by clinical investigators in terms of seriousness, severity (i.e., mild, moderate, severe) and strength of relationship (i.e., not related, unlikely related, probably related, definitely related, indeterminate) to the implant procedure, explant procedure, implant device, stimulation and Energizer. Any AE that is determined by a participating investigator to be related (definitely related or probably related) to the implant procedure, explant procedure, implant device, stimulation or Energizer will be categorized as device related.

For all AE tables, a subject reporting the same adverse event more than once will be counted once when calculating the number and percentage of subjects with that particular event. If a subject reports the same AE more than once or has the same AE on multiple occasions, the maximum severity grade and relationship to the study implant and/or study drug will be presented.

The frequencies and percentages of treatment-emergent adverse events will be presented by MedDRA system organ class (SOC) and preferred term (PT). Complete subject listings of all AE will be provided. For each AE the following will be specified: start and stop dates, severity grade, MedDRA SOC and PT, relationship (unlikely related, probably related, definitely related or indeterminate) to the implant procedure, explant procedure, implant device, stimulation or Energizer , and, as well as action taken, outcome of the adverse event, and seriousness.

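### No table shell in either SAP gives SAE incidence regardless of relatedness, although the protocol endpoint and both SAP texts call for it

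*SAP*

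**What the plan says.** **Text.** Protocol Section 8, Table 3, gives the safety endpoint as "Incidence of AEs and SAEs from informed consent to Week 264". The justification beside it refers to "The incidence of treatment emergent AEs and SAEs that are more common in the treatment group compared to control". Protocol 17.6 adds "The incidence of AEs and SAEs from informed consent to Week 264 will be tabulated". CLP-004 Section 9.1 makes the same commitment to Week 12, and CLP-008 Section 7.1 makes it to Week 264 in the safety population. None of these passages restricts SAEs by relatedness.

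**Shells.** CLP-004 Table 14.1.3.1 has an all-cause AE row with cells by arm. Its SAE block is a heading marked with footnote [1], then five rows of which the first is "Implant Procedure SAE"; the others are for implant device, stimulation, Energizer and explant procedure. Footnote [1] is "1] AEs judged to be “Definitely related” or “Probably related” are reported as “Related". CLP-008 Table 14.8.3.1 repeats the block with footnotes [4] and [5], where [4] gives the percentage base and [5] is the same definition of related.

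**Recoding.** Protocol 15.2.2 and CLP-004 Section 9.1 both state that, once treatment is unblinded, a control-arm AE reported as related to stimulation has that relationship changed to not related.

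**The concern.** Relatedness is a judgement made for each event; seriousness and randomised arm do not depend on it. The SAE comparison that randomisation protects through Week 12 is therefore SAEs of any cause, by arm. If the summary table is built from its shell, a reader sees only those SAEs that were attributed to the procedure, the device or the stimulation.

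The protocol shows that attribution can be uncertain. Section 16.2 describes a severe neutropenia in the pilot extension study that was classified as RA-related although its course coincided with changes in stimulation, so that stimulation could not be ruled out. The protocol does not say whether that event was serious. A serious event attributed in the same way in this trial would enter no SAE row.

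**Working it through.** No arithmetic from the plan needs reproducing. The check sets the commitments against the shells.

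1. **Which SAEs reach an SAE row?** Both SAPs use five relationship categories: not related, unlikely related, probably related, definitely related and indeterminate. Footnotes [1] and [5] admit two of them, so 5 − 2 = 3 categories have no SAE incidence row. Setting the footnote aside does not help: the rows are organised by attribution, so an SAE attributed to none of the five sources has no row.

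2. **Can the total be rebuilt from the five rows?** No. Relationship is assessed separately for each source, so one SAE can fall in several rows, while an unattributed SAE falls in none.

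3. **Does another table supply it?** Table 14.1.3.2 (and 14.8.3.2) covers all AEs by system organ class, preferred term and severity, without separating serious events. Tables 14.1.3.3 to 14.1.3.7 (and 14.8.3.3 to 14.8.3.7) are limited to related AEs. Tables 14.1.3.8 and 14.1.3.9 (and 14.8.3.8 and 14.8.3.9) have rows for device deficiencies and protocol deviations associated with an SAE, which are not SAE incidence.

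4. **Does severity stand in for seriousness?** No. Protocol 15.2.1 grades severity by symptoms and interference with daily activities. Protocol Section 3 defines seriousness by outcomes such as death, threat to life, hospitalisation and permanent impairment. Neither implies the other.

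5. **What does the recoding do?** Take a hypothetical pair of identical SAEs, one per arm, each reported as probably related to stimulation and to nothing else. After unblinding the stimulation row shows 1 in treatment and 0 in control, because the control event has been recoded and has left the SAE block. An all-cause row would show 1 and 1. The control cell of the stimulation row is zero by rule.

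6. **Where is seriousness still visible?** In the AE listings (16.1.2.7 and 16.8.2.8), which have an SAE column.

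**The case against.** **The SAP text governs, and the shells are mock-ups.** A reader might infer that all-cause SAE incidence will never be produced. The documents do not support that: protocol 17.6, CLP-004 9.1 and CLP-008 7.1 all commit to it. What stands is a conflict between that text and the shells that a programmer will follow.

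**The SAE heading may be meant as a total.** Heading rows in these tables are inconsistent about carrying cells, so a total may be intended. CLP-004 also places footnote [1] unevenly: among the severity blocks by attribution, only the explant block has it. In CLP-008 the marking is systematic. The all-cause AE row and the overall severity row carry [4] alone, while the related-event rows and the SAE heading carry [4] and [5]. A total under that heading would still be a total of related SAEs.

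**The events are not hidden.** This is largely right. An unrelated or indeterminate SAE counts by arm among all AEs, in the severity rows and in Table 14.1.3.2 under its preferred term. Deaths leading to withdrawal appear by arm in the disposition table, and the DMC reviews SAEs. What is lost outside the listing is the identification of these events as serious.

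**The between-arm comparison is not defined in SAP 9.1.** Correct. It comes from the justification column of Protocol Table 3. It also does not extend to the open-label period, when the control group has crossed over to active stimulation.

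**Conclusion.** The point holds as a mismatch between the stated safety endpoint and the table shells of both SAPs, and should be corrected. For CLP-004 there are two reasons: the endpoint is not tabulated as promised, and the related-only rows cannot serve as the randomised SAE comparison through Week 12, because of the recoding. For CLP-008 the only reason is consistency with the stated endpoint.

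The size is three of five relationship categories without an SAE incidence row. A reader might want a figure in subjects from the earlier long-term study in 18 patients, where "Nine subjects experienced an SAE, but only 1 SAE was deemed to be device related". The documents do not support carrying that over. The study was uncontrolled, used a different device, allowed biologics and ran until the last patient had completed 48 months. Its report gives no count of procedure-related SAEs, which would have rows here. In SPM-005, the preceding study with stimulation to Day 84, the same 18 patients had no serious AEs. The number of SAEs affected by Week 12 is therefore unknown and could be small.

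The conclusion assumes that the shells will be programmed as written, with footnotes [1] and [5] applied to the SAE block.

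**What to change.** In CLP-004 Table 14.1.3.1 and CLP-008 Table 14.8.3.1, begin the SAE block with a row labelled *Any SAE, regardless of relationship*, giving events, n and % by group and overall, without footnote [1] or [5]. Keep the five attribution rows beneath it, labelled as a subset, with the footnote attached to them. A table of SAEs by system organ class and preferred term would be a useful optional addition; neither document promises one.

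The cost is a wording change in two shells, plus one repeated shell per SAP if the optional table is added. Seriousness is already assessed for every AE and listed, so no new data are needed, and no efficacy test or error rate is affected. The change should be made before lock, because Section 5.1 of each SAP treats analyses designed afterwards as post hoc.

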Baseline	Information and values collected during Screening. The RA disease activity assessments that serve as the baseline assessments used for determination of the primary and key secondary efficacy endpoints must be performed on the day of informed consent.
CDAI	
The CDAI score is based on 4 items:
 
 • TJC28 • SJC28

Term	Definition
	
 SGA EGA 
The CDAI score is calculated as follows and ranges from 0 to 76:
 
 CDAI = TJC28 + SJC28 + SGA + EGA 
The CDAI score corresponds to the current RA activity:
 
 0 to \leq 2.8 Remission >2.8 to \leq 10 Low disease activity (LDA) >10 to \leq 22 Moderate disease activity > 22 High disease activity 
The MCID is a score reduction by 12 if starting in high activity, 6 if starting in moderate activity, and 1 if starting in low activity.

Control to Open Label (COL) population	Control subjects from ITT population who received non-active (sham) stimulation through Week 12, switched to active stimulation after completing Week 12 assessments, continued to receive active stimulation during open-label follow-up, and for whom follow-up data are available.
Crossover	The process of switching from an initially assigned treatment to the other treatment being studied.
DAS28-CRP	
The DAS28-CRP score is a composite index providing a measure of disease activity, comprising:
 
 TJC28 SJC28 SGA hsCRP (mg/L) 
A total score ranges from 0 to 10 and is computed as follows:
 $\text{DAS28-CRP} = 0.56 * \text{sqrt}(\text{TJC28}) + 0.28 * \text{sqrt}(\text{SJC28}) + 0.36 * \ln(\text{CRP}+1) + 0.014 * \text{SGA} + 0.96$ 
The DAS28-CRP score corresponds to the current RA activity:
 
 0 to $<$ 2.6 Remission 2.6 to $<$ 3.2 LDA 3.2 to \leq 5.1 Moderate activity > 5.1 High activity 
A DAS28-CRP score reduction by 1.2 represents the MCID.

Day 0 (randomization, initiation of stimulation)	
Scheduled study visit occurring 14 to 21 days after Implant Procedure during which subjects undergo the following study procedures in the order specified:
 
 Day 0 assessments Randomization Initiation of stimulation 
Subjects must receive final surgical clearance with an approval to initiate study treatment before proceeding to the Day 0 visit.

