Device deficiency	Inadequacy of a medical device with respect to its identity, quality, durability, reliability, safety or performance. Device deficiencies include malfunctions, use errors, and inadequate labeling. [BS EN ISO 14155]

Term	Definition
Device malfunction	Failure of an investigational medical device to perform in accordance with its intended purpose when used in accordance with the instructions for use or clinical investigation protocol. [BS EN ISO 14155]
DMC	An independent data monitoring committee responsible for safeguarding the interests of study participants, assessing the safety and efficacy of the interventions during the study, and for monitoring the overall conduct of the clinical study.
EGA	A global assessment of the subject's RA activity performed by an independent, blinded Joint Evaluator using NRS from 0 (inactive) to 10 (very active).
EQ-5D-5L	
A standardized instrument for measuring general health status within the following 5 dimensions:
 
 • Mobility • Self-care • Usual activities • Pain/discomfort • Anxiety/depression 
Each dimension is scored on 5-point scale as:
 
 • No problems • Slight problems • Moderate problems • Severe problems • Extreme problems 
In addition, general health status is scored from 0 (the worst health) to 100 (the best health).

Enrolled	Subjects meeting all the inclusion and none of the exclusion criteria in whom the implant procedure is attempted.
EULAR response criteria	
A means of measuring efficacy of treatment using DAS28-CRP, incorporating both an absolute measure of disease activity, and a measure of change in activity.
 
A subject is considered having a moderate treatment response if:
 
 • DAS28-CRP score improvement from baseline to Week 12 is > 0.6 and ≤ 1.2, and the DAS28-CRP score at Week 12 is ≤ 5.1; or • DAS28-CRP score improvement from baseline to Week 12 is > 1.2, and the DAS28-CRP score at Week 12 is > 3.2. 
A subject is considered having a good treatment response if:
 
 • DAS28-CRP score improvement from baseline to Week 12 is > 1.2 and the DAS28-CRP score at Week 12 is ≤ 3.2
Flare	Worsening of RA symptoms resulting in an increase between consecutive visits in DAS28 score ≥ 1.2 , or an increase ≥ 0.6 if the first of the paired visits had DAS28 ≤ 3.2 .

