17.8 Analysis Populations

The interim and primary efficacy analyses at Week 12 will be conducted on the intent-to-treat (ITT) population. Exploratory analyses will be performed on the ITT and per-treatment-evaluable (PTE) populations through Week 12 and on the open-label and cross-over PTE populations during the open-label, long-term follow-up. The safety will be evaluated on the safety population. All analysis populations are defined below:

- *ITT population.* All enrolled and randomized subjects in Stage 1 and 2.
- *PTE population.* Subjects from ITT population who received the assigned treatment through Week 12, have no major procedural protocol deviations (see Section 18.2.2), and for whom follow-up data through Week 12 are available.
- *Treatment to Open Label (TOL) population.* Treatment subjects from ITT population who received active stimulation through Week 12, completed Week 12 assessments, continued to receive active stimulation during open-label follow-up, and for whom follow-up data are available.
- *Control to Open Label (COL) population.* Control subjects from ITT population who received non-active (sham) stimulation through Week 12, switched to active stimulation after completing Week 12 assessments, continued to receive active stimulation during open-label follow-up, and for whom follow-up data are available.
- *Safety population.* All enrolled subjects.

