5.2 Analysis Populations

Analysis population defines the subjects to be included in an analysis. The primary efficacy analyses for the primary and key secondary endpoints will be conducted on the intent-to-treat (ITT) and per-treatment-evaluable (PTE) populations. The exploratory analyses will be conducted on the ITT population as detailed in **Table 4**. All analysis populations are defined below:

- *ITT population.* All enrolled and randomized subjects in Stage 1 and 2.
- *PTE population.* Subjects from ITT population who have received the assigned treatment, who have no major procedural protocol deviations (see Section 9.2) and for whom follow-up data are available.
- *Safety population.* All enrolled subjects in Stage 1 and 2.

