Preferred Term 2	xx x (xx%)	xx x (xx%)	xx x (xx%)	xx x (xx%)	xx x (xx%)	xx x (xx%)	xx x (xx%)	xx x (xx%)	xx x (xx%)	xx x (xx%)	xx x (xx%)	xx x (xx%)
Preferred Term 3	xx x (xx%)	xx x (xx%)	xx x (xx%)	xx x (xx%)	xx x (xx%)	xx x (xx%)	xx x (xx%)	xx x (xx%)	xx x (xx%)	xx x (xx%)	xx x (xx%)	xx x (xx%)
Preferred Term 4	xx x (xx%)	xx x (xx%)	xx x (xx%)	xx x (xx%)	xx x (xx%)	xx x (xx%)	xx x (xx%)	xx x (xx%)	xx x (xx%)	xx x (xx%)	xx x (xx%)	xx x (xx%)
System Organ Class 2 [1,2]	xx x (xx%)	xx x (xx%)	xx x (xx%)	xx x (xx%)	xx x (xx%)	xx x (xx%)	xx x (xx%)	xx x (xx%)	xx x (xx%)	xx x (xx%)	xx x (xx%)	xx x (xx%)
Preferred Term 1	xx x (xx%)	xx x (xx%)	xx x (xx%)	xx x (xx%)	xx x (xx%)	xx x (xx%)	xx x (xx%)	xx x (xx%)	xx x (xx%)	xx x (xx%)	xx x (xx%)	xx x (xx%)
Preferred Term 2	xx x (xx%)	xx x (xx%)	xx x (xx%)	xx x (xx%)	xx x (xx%)	xx x (xx%)	xx x (xx%)	xx x (xx%)	xx x (xx%)	xx x (xx%)	xx x (xx%)	xx x (xx%)
Preferred Term 3	xx x (xx%)	xx x (xx%)	xx x (xx%)	xx x (xx%)	xx x (xx%)	xx x (xx%)	xx x (xx%)	xx x (xx%)	xx x (xx%)	xx x (xx%)	xx x (xx%)	xx x (xx%)
Preferred Term 4	xx x (xx%)	xx x (xx%)	xx x (xx%)	xx x (xx%)	xx x (xx%)	xx x (xx%)	xx x (xx%)	xx x (xx%)	xx x (xx%)	xx x (xx%)	xx x (xx%)	xx x (xx%)

Continue to report all
reported events

CONFIDENTIAL

123 of 158

May not be reproduced outside of SetPoint Medical without written permission from Document Control.

Abbreviations: AE, adverse event; SOC, system organ class.

Note: AEs coded using the MedDRA dictionary Version 21.0 or later. Given in the table are subject counts and percentages. At each level of summation, subjects are counted only once. Subjects experiencing AEs of more than one severity are summarized according to the maximum severity experienced over all episodes of an AE.

[1] Percentage calculated based on ITT Population.

[2] AEs judged to be “Definitely Related” or “Probably Related” to Implant Procedure are reported.

Reference: Listing 16.x.x.x

SOURCE: xxxxx SAS 9.4 {program location} {run date/time} }

Table 14.1.3.4
Implant Device-Related Adverse Events by SOC and Maximum Severity: All Events
(Safety Population)

Repeat Table 14.1.3.4 for implant device-related adverse events

Table 14.1.3.5
Stimulation-Related Adverse Events by SOC and Maximum Severity: All Events
(Safety Population)

Repeat Table 14.1.3.4 for stimulation-related adverse events

Table 14.1.3.6
Explant Procedure-Related Adverse Events by SOC and Maximum Severity: All Events
(Safety Population)

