Repeat Table 14.1.3.4 for explant procedure-related adverse events

Table 14.1.3.7
Energizer-Related Adverse Events by SOC and Maximum Severity: All Events
(Safety Population)

Repeat Table 14.1.3.4 for Energizer-related adverse events

Table 14.1.3.8
 Device Deficiency
 (Safety Population)

Variable	Treatment (N=xxx)		Control (N=xxx)		All (N=xxx)	
	Events	n (%)	Events	n (%)	Events	n (%)
Any study device deficiency [1]	xx	xx (xx.x%)	xx	xx (xx.x%)	xx	xx (xx.x%)
Relationship of study device deficiency [1]						
MicroRegulator (Implant)	xx	xx (xx.x%)	xx	xx (xx.x%)	xx	xx (xx.x%)
POD	xx	xx (xx.x%)	xx	xx (xx.x%)	xx	xx (xx.x%)
Energizer	xx	xx (xx.x%)	xx	xx (xx.x%)	xx	xx (xx.x%)
Stimulation	xx	xx (xx.x%)	xx	xx (xx.x%)	xx	xx (xx.x%)
Prescription Pad	xx	xx (xx.x%)	xx	xx (xx.x%)	xx	xx (xx.x%)
IFU/Labeling	xx	xx (xx.x%)	xx	xx (xx.x%)	xx	xx (xx.x%)
Study device deficiency associated with AE [1]	xx	xx (xx.x%)	xx	xx (xx.x%)	xx	xx (xx.x%)
Study device deficiency associated with SAE [1]	xx	xx (xx.x%)	xx	xx (xx.x%)	xx	xx (xx.x%)

Abbreviations: AE, adverse event; POD, Positioning Orientation Device; SAE, serious adverse event.

Note: Given in the table are subject counts and percentages. At each level of summation, subjects are counted only once. Subject experiencing several episodes of the same type of study device deficiency is counted once.

[1] Percentage calculated based on safety ITT population.

Reference: Listing 16.x.x.x

SOURCE: xxxxx SAS 9.4 {program location} {run date/time} }

Table 14.1.3.9
Protocol Deviations
(ITT Population)

Variable	Treatment (N=xxx)		Control (N=xxx)		All (N=xxx)	
	Events	n (%)	Events	n (%)	Events	n (%)
Any protocol deviations [1]	xx	xx (xx.x%)	xx	xx (xx.x%)	xx	xx (xx.x%)
Any major procedural protocol deviations	xx	xx (xx.x%)	xx	xx (xx.x%)	xx	xx (xx.x%)
Consent not obtained prior to initiating any study-related procedures	xx	xx (xx.x%)	xx	xx (xx.x%)	xx	xx (xx.x%)
Received study treatment not consistent with the treatment assignment	xx	xx (xx.x%)	xx	xx (xx.x%)	xx	xx (xx.x%)
Subject not eligible received treatment procedure	xx	xx (xx.x%)	xx	xx (xx.x%)	xx	xx (xx.x%)
Minor protocol deviations [1]	xx	xx (xx.x%)	xx	xx (xx.x%)	xx	xx (xx.x%)
Improper documentation of consent	xx	xx (xx.x%)	xx	xx (xx.x%)	xx	xx (xx.x%)
Visit or assessment not done	xx	xx (xx.x%)	xx	xx (xx.x%)	xx	xx (xx.x%)
Visit or assessment completed out of window	xx	xx (xx.x%)	xx	xx (xx.x%)	xx	xx (xx.x%)

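### Adverse-event tables titled Safety Population footnote their percentages to the ITT population, so the All-column percentages have the wrong or an unclear denominator

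*SAP*

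**What the plan says.** SAP 5.2 defines the Safety population as "All enrolled subjects in Stage 1 and 2" and the ITT population as "All enrolled and randomized subjects in Stage 1 and 2". Protocol Section 3 defines enrolled as "Subjects meeting all the inclusion and none of the exclusion criteria in whom the implant procedure is attempted". Protocol 17.8 states: "The safety will be evaluated on the safety population".

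Randomisation comes 14 to 21 days after the implant, and Protocol Section 3 makes it conditional: "Subjects must receive final surgical clearance with an approval to initiate study treatment before proceeding to the Day 0 visit". SAP 5.5 confines randomisation to enrolled subjects who were implanted, and SAP 6.1 summarises attempted and successful implants separately.

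The SAP Appendix B safety shells, all titled Safety Population, treat the denominator as follows:

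- Table 14.1.3.1 (overall AE and SAE summary): no ITT footnote. Its footnote [1] concerns relatedness.
- Tables 14.1.3.2 (all AEs) and 14.1.3.3 (implant-procedure-related AEs): "1] Percentage calculated based on ITT Population".
- Tables 14.1.3.4 to 14.1.3.7: no footnote of their own. Table 14.1.3.4 says "Repeat Table 14.1.3.4 for implant device-related adverse events", so it refers to itself, and the other three repeat the same table number.
- Table 14.1.3.8 (device deficiency): "1] Percentage calculated based on safety ITT population".

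The long-term SAP's matching tables (14.8.3.1 to 14.8.3.3) take percentages on each analysis population in its own right, Safety included.

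**The concern.** A table titled for one population whose percentages are based on another cannot be programmed as written without departing from either the title or the footnote. The two populations differ by the subjects who had an implant attempted but were never randomised. Such subjects are foreseeable: the implant may fail, or surgical clearance may be withheld. Because clearance decides who goes on to randomisation, this group may be enriched for surgical complications.

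Procedure risk is a central safety question for an implanted device. Protocol 7.3.2 reports 6 procedure-related events among 14 pilot subjects, including a vocal cord paralysis and a Horner's syndrome. The Week 12 data are meant to support the PMA application. Table 14.1.3.3, the detailed procedure-related table, is one of the two with the plain ITT footnote.

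**Working it through.** The plan states no safety rate, so there is no figure to reproduce. The check compares definitions with footnotes and then works out the consequence.

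**Does another passage settle the denominator?** SAP 9.1 names none. SAP 5.1 says percentages use n, but does not say which population supplies n for these tables. The footnote is therefore the specific instruction a programmer would follow, and in Tables 14.1.3.2 and 14.1.3.3 it conflicts with the title, with the SAP 5.2 definitions and with Protocol 17.8.

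**Which columns can change?** The shells have Treatment, Control and All columns. A subject who was never randomised has no assigned arm, so only All is affected.

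**Inputs**

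- N = 250 randomised (SAP 5.5 allows 240 to 250).
- k = number enrolled but not randomised. Not in the documents; assumed range 1 to 25.
- x = 25 randomised subjects with the event (assumption).
- y = non-randomised subjects with the event, from 0 to k (assumption).

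**Formulas for the All column**

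- A, Safety count over Safety denominator (as defined): (x + y)/(N + k)
- B, Safety count over ITT denominator (the footnote taken literally): (x + y)/N
- C, ITT count over ITT denominator: x/N

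B/A = (N + k)/N = 1 + k/N, whatever x and y are. For N = 250 this is 1.004 at k = 1, 1.04 at k = 10 and 1.10 at k = 25.

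| k | y | A | B | C |
|---|---|---|---|---|
| 1 | 1 | 26/251 = 10.4% | 26/250 = 10.4% | 25/250 = 10.0% |
| 10 | 0 | 25/260 = 9.6% | 25/250 = 10.0% | 10.0% |
| 10 | 10 | 35/260 = 13.5% | 35/250 = 14.0% | 10.0% |
| 25 | 0 | 25/275 = 9.1% | 25/250 = 10.0% | 10.0% |
| 25 | 25 | 50/275 = 18.2% | 50/250 = 20.0% | 10.0% |

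B always overstates A. C understates A only when the event rate among non-randomised subjects exceeds x/N. At k = 10 the break-even is y = 10 × 25/250 = 1, where A = 26/260 = 10.0% = C.

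**The case against.** The strongest reply is that this is carried-over template text rather than an analysis decision. The same ITT footnote sits under Tables 14.1.2.1.0 and 14.1.2.2.1, which are titled PTE Population, and the safety ITT phrase recurs under Table 14.1.3.9, which is titled ITT. The body text is clear about who belongs to the Safety population. That probably explains where the footnotes came from, but it does not remove the contradiction, because no general rule in the SAP overrides them.

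Other parts of the reply stand and limit the point:

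- A reader might infer that non-randomised subjects are dropped from the safety tables. The documents do not say so. The footnote sets the denominator, not who is counted; the titles say Safety; the AE shells ask for all reported events; and the programming note to Listing 16.1.2.1.1 keeps all enrolled subjects in the other listings. Loss of events is a possible programming outcome, not an instruction.
- A reader might infer that every safety table is affected. Table 14.1.3.1 has no ITT footnote and already reports implant-procedure-related AEs, their maximum severity and implant-procedure SAEs. For Tables 14.1.3.4 to 14.1.3.7 the ITT denominator is an inference, and Table 14.1.3.8 is ambiguous rather than plainly ITT.
- A reader might infer that this group is the most exposed to surgical harm. Every enrolled subject undergoes an attempted implant, so exposure to the procedure is common to all. Possible enrichment for complications is as far as the documents go.
- The denominator can be recovered, since Table 14.1.1.1 reports enrolled, implanted, randomised, ITT and Safety counts.

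**Conclusion.** The point holds as an internal contradiction that should be corrected. It is certain in Tables 14.1.3.2 and 14.1.3.3, an ambiguity in Table 14.1.3.8, and inherited by Tables 14.1.3.4 to 14.1.3.7 if their repeat instruction means Table 14.1.3.3. The All percentage in Table 14.1.3.3 could also disagree with the corresponding row of Table 14.1.3.1 for the same events.

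The treatment-versus-control safety comparison is untouched. Taken literally, the footnote overstates the All percentage by k/250 in relative terms, which is small unless many subjects go unrandomised. A marked understatement, such as 10.0% for 13.5%, needs two further assumptions: that counts are also restricted to ITT, and that events are concentrated in the non-randomised group (all 10 of 10 in that example). Neither can be established from the documents, and k is unknown, so no single figure for the error can be given.

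**What to change.** Change the footnotes of Tables 14.1.3.2, 14.1.3.3 and 14.1.3.8 so that percentages are based on the Safety population, as the long-term SAP already does. Point the repeat instructions for Tables 14.1.3.4 to 14.1.3.7 to Table 14.1.3.3. State that enrolled, non-randomised subjects, including those with unsuccessful implants, are counted in the All column. Resolve the undefined phrase under Table 14.1.3.9 in the same edit.

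For Table 14.1.3.5, add a note that stimulation starts only after randomisation. Non-randomised subjects were never at risk of stimulation-related events, and including them slightly dilutes the All percentage there.

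The cost is a few footnotes, corrected table references and one denominator setting. No new data or analysis is needed.
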